### 5.1.2. Analysis of Adverse Events

AEs (unsolicited and solicited AEs) will be tabulated by presenting the number and percentage of subjects having at least one of the observed AEs.

The unsolicited AEs will be summarized by System Organ Class and Preferred Term. The solicited AEs will be summarized by class (local, systemic) and solicited term. For solicited as well as unsolicited AEs, tables focusing on severity, relatedness and both grade 3 severity and relatedness to vaccine will be created. SAEs, AEs with fatal outcome and AEs leading to permanent stop will also be tabulated. Separate summary tables for the solicited and the unsolicited events will be produced.

Events of interest (confirmed HIV infection) will be tabulated.

For the solicited local and systemic AEs, the duration and time to first onset of the events may also be summarized. If a subject experiences more than one occurrence of a solicited event, the maximum duration of the events will be used. The time to first onset is defined as (date of first onset – reference date + 1). The reference date is the date of the respective vaccination.

AEs summary tables for solicited and unsolicited AEs, tabulation of AEs by worst severity for the solicited AEs and overall incidence tabulation will be provided by subgroups (section 2.4) per period by regimen.

### 5.1.3. Period Allocation of Adverse Events

The analysis of AEs consists of two steps: first, AEs are allocated to periods; second, overlapping/consecutive AEs within a period are combined.

Unless otherwise specified, only emerging AEs are presented and are allocated to the periods as described below.

Solicited AEs will always be considered as emergent, and will be allocated to the respective post-dose x periods.

In the below text active periods refer to the post-dose x (x=1,2,3,4) and the regimen period. The post-dose 1 period (and the regimen period) are considered as first active period.

#### STEP 1: allocation of events to the periods

Adverse events present in the SDTM database are allocated to periods based on their start date. If the start date of an event falls between (or on) the start and stop date of a period, the AE is attributed to that period.

Incomplete dates (i.e. *day and/or month and/or year missing*):

- In case of partial start or stop dates, the events are allocated to the periods using the available partial information on start and end date, no imputation is done. If, for instance, for the AE start date only month and year is available, these data are compared with the month and year info of the periods. This rule may lead to multiplication of the event as a consequence of its assignment to multiple periods.
- In case of a completely missing end date, the date is imputed by the cut-off date of the analysis for subjects still ongoing in the study, and by the end date of the last period for subjects who discontinued or completed the trial.

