9.3.2. Evaluations

Any clinically relevant safety-related changes that occur during the study must be recorded in the CRF.

Any clinically significant abnormalities persisting at the end of the study/early withdrawal will be followed by the investigator until resolution or until a clinically stable endpoint is reached.

The study will include the following evaluations of safety and tolerability according to the time points provided in the Time and Events Schedule:

Adverse Events

AEs will be recorded from signing of ICF until the final visit of the main study (Week 96). SAEs (including HIV infection and abnormal pregnancy outcome) will be recorded for the duration of the study, including the optional LTE phase (Group 1 and Group 2 only). AEs will be followed by the investigator as specified in Section 12.

Details regarding the PSRT and the DMC are provided in Sections 11.7 and 11.8, respectively.

Cardiac-Related Events

At study visits, subjects will be specifically questioned about cardiac-related events, including chest pain/pressure, shortness of breath, and peripheral edema. Any suspicion of a cardiac event will be evaluated clinically by history and physical examination, ECG (read by a central reading cardiologist), and quantitative troponin assay. In the event of an elevation of troponin and/or pathologic ECG changes, the subject will be sent for evaluation by a local cardiologist.

Solicited Adverse Events

Solicited AEs are precisely defined events that subjects are specifically asked about and which are noted by subjects through the memory aid. The investigator or his/her designee should discuss the information from the memory aids with subjects, document relevant information in the clinic chart (source document) and complete the relevant parts of the CRF as described in the CRF Completion Guidelines.

Injection Site (Local) Reactions

Subjects will be asked to note occurrences of erythema, induration and swelling (measured using the ruler supplied), and pain/tenderness, itching, or warmth at the injection site daily for 8 days post-vaccination (day of vaccination and the subsequent 7 days). These occurrences should be recorded through the memory aid provided to serve as a reminder to the subject for the next clinic visit.

Solicited Systemic AEs

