### 5. SAFETY

The safety and tolerability endpoints are:

- Unsolicited AEs 28 days following each vaccination
- Solicited local and systemic AEs (reactogenicity), collected daily from day of vaccination for 7 days post-vaccination (day of vaccination and the subsequent 7 days).

The safety and tolerability analysis will be performed on the FA set. Specifically, the analysis for solicited adverse events will be done on those subjects in the FA set for whom reactogenicity assessments are available in the database (either via on-site assessments or via the diary pages of the CRF).

Safety data will be tabulated per period by regimen. Only the active periods will be shown in the tables (AE, Lab, VS and ECG), except for SAEs and HIV infections. In addition, for a selection of tables (AE, Lab), tabulations per subject by vaccine and per dose by vaccine will be provided. During the LTE only for SAEs and HIV infections will be collected.

In the 'per subject by vaccine' analysis, the safety will be presented per periods (post-dose 1, 2, 3, 4) by vaccine rather than by regimen. A 'post any dose' period (= regimen phase in section 2.1) will be added, that summarizes the safety after all administered doses of a vaccine. The post-any-dose period allows determining how many subjects reported events after administration of a certain vaccine regardless the number of doses. Each subject is counted only once. In case a subject has the same event after more than one dose, it is counted only once (and in case of showing attributes, the worst corresponding attribute is shown) in the post-any dose period. The denominator is the number of subjects that received the considered vaccine in the considered period.

In the 'per dose by vaccine' analysis, the safety will also be presented by vaccine. This table allows determining the incidence of events per administered dose of a certain vaccine. For example, if a subject has the same event at least

once after dose 1 and at least once after dose 2 of the same vaccine, it is counted 2 times (so the numerator is the sum of post-dose 1, 2, 3 and 4 events in the “per subject by vaccine” table). In case of showing attributes, the worst corresponding attribute of each period are shown. The denominator is the total number of doses administered of the considered vaccine over all subjects.

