#### STEP 2: combining events

Overlapping/consecutive events are defined as events in the same subject with the same preferred term which have at least 1 day in overlap or for which the start date of an event is 1 day after the end date of the preceding event. Overlapping/consecutive events may be combined into one AE or not, according to the following rules:

- 1) In case a non-active period (e.g. Screening) is followed by an active period, and the overlapping/consecutive events start in both periods, they are allocated to their respective period and are considered as separate events.
- 2) In case overlapping/consecutive events start within a single period, they are considered as one and the same AE. The individual events that contribute to this AE are retained as individual records in the ADAM database but are assigned the same onset, period, and total duration.
- 3) In case an active period is followed by a non-active period (e.g. Follow-Up), and the overlapping/consecutive events start in both periods, they are allocated to the active period and are considered as one and the same AE. The individual events that contribute to this AE are retained as individual records in the ADAM database but are assigned the same duration, onset and active period.
- 4) In case an active period is followed by an active period, and the overlapping/consecutive events start in both periods, they are allocated to their respective period and are considered as separate AEs. The same rule applies for 2 non-active periods.

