#### Remarks:

1. Events can only be combined into one and the same AE if their start and stop dates are complete.
2. In case the completely missing end date is imputed (for phase allocation), this date is also considered as a complete date.
3. Time during the day is not considered when determining overlap of events.
4. Solicited AEs will never be attributed to the Screening Phase

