### 5.1.4. Handling of Missing Data for Adverse Events

Missing data will not be imputed. If the severity is missing for a solicited AE, then it is considered as unknown and not taken into account for the analysis.

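### The SAP gives an adverse event with no end date an artificial one and does not keep that date out of the solicited-reaction duration summary

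*SAP*

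**What the plan says.** - **Collection.** Protocol 9.3.2 and SAP Section 5 have subjects note solicited reactions on the day of vaccination and the next 7 days, 8 days in all. Protocol 9.3.2 also has the investigator follow AEs, with recording up to Week 96.
- **Imputation.** SAP 5.1.3, STEP 1: "In case of a completely missing end date, the date is imputed by the cut-off date of the analysis" for subjects still ongoing. For subjects who discontinued or completed, the end of the last period is used. Partial dates are not imputed.
- **Status of the imputed date.** Remark 2 in SAP 5.1.3 links the imputation to phase allocation in a parenthesis and then says "this date is also considered as a complete date".
- **Combining records.** Under STEP 2, rule 2, the records that make up one combined event "are assigned the same onset, period, and total duration". Rule 3 likewise gives them a common duration.
- **Duration summary.** SAP 5.1.2 says of solicited events that "the duration and time to first onset of the events may also be summarized", and: "If a subject experiences more than one occurrence of a solicited event, the maximum duration of the events will be used". It gives no formula for duration, no cap and no rule for unresolved events.
- **Missing data.** SAP 5.1.4: "Missing data will not be imputed".

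**The concern.** An end date set at the analysis cut-off or at the last visit carries no information on how long a sore arm or a headache lasted. It is harmless if it only helps to sort records. It is not harmless if it becomes the end point of a duration, because the result then measures time on study. Taking the subject's maximum makes this worse: where a subject also has genuine durations of the same event, the artificial one is selected.

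At stake is one descriptive table of reactogenicity. Safety and tolerability is a primary objective, and Protocol 11.9 (Table 8, third footnote) gives persistence beyond 72 hours a role in the pause rule for Grade 3 solicited events, so readers will take an interest in duration. The pause rule itself runs on investigator notification and does not depend on this table.

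**Working it through.** **1. What the imputed end date does for a solicited event.** STEP 1 allocates events by start date, and SAP 5.1.3 assigns solicited events to their own post-dose period in any case. With a known start, the imputed end therefore plays no part in allocation. Its remaining use is STEP 2. Remark 1 lets records be combined only when start and stop dates are complete, and Remark 2 lets the imputed date qualify. Because the imputed end lies so late, an open record overlaps every later record of the same preferred term in that subject. Rule 2 (same period) or rule 3 (an active period followed by a non-active one) then merges them and assigns a common duration. Rule 4 keeps apart events that start in two active periods. So the route to duration is in the text for combined records. For a single open record the SAP neither states it nor excludes it.

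**2. Size of one imputed duration.** Inputs: nominal visit days from Protocol 9.1.2; SAP Table 3 with its note c, which ends the last period at the last visit, intended to be Week 96, with a main-study cut-off of 29 August 2017.

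Study day = 7 × week + 1 reproduces the protocol's figures: Week 12 = Day 85, Week 24 = Day 169, Week 48 = Day 337, Week 96 = Day 673.

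Duration = end day − onset day + 1. The SAP gives no duration formula; this inclusive count is an assumption that mirrors its formula for time to first onset. With onset on the vaccination day and end at Day 673:

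| Dose | Onset day | Duration (days) |
|---|---|---|
| 1 | 1 | 673 − 1 + 1 = 673 |
| 2 | 85 | 673 − 85 + 1 = 589 |
| 3 | 169 | 673 − 169 + 1 = 505 |
| 4 | 337 | 673 − 337 + 1 = 337 |

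These are nominal values, not ceilings. The Week 96 window of +3 weeks allows Day 673 + 21 = 694, hence 694 days from dose 1. For subjects who take the cut-off date instead, a dose 1 given before 27 October 2015 would also exceed 673 days. Enrolment dates are not in the documents.

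**3. Effect on a group summary.** The documents give no reaction durations, no number of reactors and no number of open records, so what follows is illustrative. Assume 50 durations in a group, k of them open with imputed duration d, the rest 2 days.

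Mean = ((50 − k) × 2 + k × d) / 50

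- k = 1, open record held at 8 days: (98 + 8)/50 = 2.1 days
- k = 1, d = 673: (98 + 673)/50 = 15.4 days
- k = 1, d = 505: (98 + 505)/50 = 12.1 days
- k = 3, d = 673: (94 + 2019)/50 = 42.3 days
- k = 3, d = 505: (94 + 1515)/50 = 32.2 days

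With one outlying value the sample SD is (d − 2)/√50, which is 671/7.07 = 95 days for dose 1 and 503/7.07 = 71 days for dose 3. The median stays at 2 days throughout.

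The result does not hang on the 2 days. With 49 durations of 3 days, one open dose 1 record moves the mean from (147 + 8)/50 = 3.1 to (147 + 673)/50 = 16.4. With the other 49 anywhere from 1 to 8 days, the mean with one such record is 14.4 to 21.3 days.

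**The case against.** The best defence is that the SAP never says an imputed end date enters the duration summary. The rule sits in a section on period allocation, Remark 2 gives phase allocation as its purpose, and 5.1.4 can be read as the general rule that governs everything else, including duration. The summary is optional. Duration is not an endpoint: Protocol 9.3.1 lists AEs, reactogenicity rates, discontinuations due to AEs and SAEs, and no safety testing is planned.

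Much of this stands. It does not close the gap, because allocation of a solicited event with a known start needs no end date, and STEP 2 does assign a duration to combined records after Remark 2 has admitted the imputed date. For single records, two programmers could reasonably do different things.

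A reader might go further in four ways that the documents do not support:

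- *That the 8-day memory aid itself leaves reactions open.* Memory aids are reviewed with the subject (Protocol 17.4), and AEs are followed beyond Day 8, so a later end date can be recorded. Only a completely missing end date triggers the rule.
- *That every open reaction is certain to be counted to Week 96.* The text carries this only for combined records.
- *That 673 days is the maximum.* It is a nominal value.
- *That the artefact could sway the choice of regimen.* Nothing in the plan uses reaction duration to separate regimens; the protocol synopsis puts the emphasis on the strength and breadth of Env antibody responses.

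**Conclusion.** The point holds as a gap and an inconsistency within the SAP, not as a demonstrated error in a result. Sections 5.1.3 and 5.1.4 disagree on their face, and nothing in 5.1.2 prevents an imputed end date from being used as the end of a reaction. Followed as written, an open reaction merged with another record carries hundreds of days into the optional duration summary. A single open record would do the same if the imputed date were also used there.

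The damage would fall on the mean, SD and maximum. Even one such record in 50 would raise the mean several-fold under the assumptions above. The median is essentially unaffected, and so are the incidence and severity tables. How often end dates were completely missing is unknown, and the SAP does not say which statistics a duration table would show. Mean, SD and maximum are in its list for continuous variables in Section 4, but that list is given for subject information.

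**What to change.** - In SAP 5.1.2 and 5.1.3, state that an imputed end date serves allocation and overlap only and is never used to compute a duration, for single or combined records.
- Show solicited events with no end date as ongoing, censored at the last day on which the event was recorded as present. Report median and quartiles with the number censored.
- Reword 5.1.4 so that it names the exception made in 5.1.3.
- SAP Section 1 says the Week 96 analysis is done and will not be rerun, and in the extension only SAEs and HIV infections are collected. New text alone would therefore change nothing already produced. Check whether a duration table exists, how open records were derived in it, and correct or footnote it if imputed ends were used. If there is no such table, the text change is enough.

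The cost is a few sentences and one check of existing output, plus a footnote or a corrected table if needed. The downside is that unresolved reactions appear as censored values rather than as a number of days.

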#### STEP 2: combining events

Overlapping/consecutive events are defined as events in the same subject with the same preferred term which have at least 1 day in overlap or for which the start date of an event is 1 day after the end date of the preceding event. Overlapping/consecutive events may be combined into one AE or not, according to the following rules:

- 1) In case a non-active period (e.g. Screening) is followed by an active period, and the overlapping/consecutive events start in both periods, they are allocated to their respective period and are considered as separate events.
- 2) In case overlapping/consecutive events start within a single period, they are considered as one and the same AE. The individual events that contribute to this AE are retained as individual records in the ADAM database but are assigned the same onset, period, and total duration.
- 3) In case an active period is followed by a non-active period (e.g. Follow-Up), and the overlapping/consecutive events start in both periods, they are allocated to the active period and are considered as one and the same AE. The individual events that contribute to this AE are retained as individual records in the ADAM database but are assigned the same duration, onset and active period.
- 4) In case an active period is followed by an active period, and the overlapping/consecutive events start in both periods, they are allocated to their respective period and are considered as separate AEs. The same rule applies for 2 non-active periods.

#### Remarks:

1. Events can only be combined into one and the same AE if their start and stop dates are complete.
2. In case the completely missing end date is imputed (for phase allocation), this date is also considered as a complete date.
3. Time during the day is not considered when determining overlap of events.
4. Solicited AEs will never be attributed to the Screening Phase

### 5.1.4. Handling of Missing Data for Adverse Events

Missing data will not be imputed. If the severity is missing for a solicited AE, then it is considered as unknown and not taken into account for the analysis.

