9.3. Safety Evaluations

9.3.1. Endpoints

Safety and tolerability endpoints:

- AEs until Week 96 and local and systemic reactogenicity rates for 8 days after each vaccination.
- Discontinuations from vaccination/from study due to AEs.
- SAEs during the course of the study.

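### As written, SAP 5.1.4 removes ungraded solicited AEs from all tables, not only by-grade ones; this conflicts with Protocol 11.5 and can only lower any-grade reactogenicity

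*SAP*

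**What the plan says.** SAP Section 5.1.4 opens with "Missing data will not be imputed" and continues: "If the severity is missing for a solicited AE, then it is considered as unknown and not taken into account for the analysis". The exclusion is written for solicited AEs only; unsolicited AEs have no matching rule.

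SAP Section 5.1.2 has solicited and unsolicited AEs "tabulated by presenting the number and percentage of subjects having at least one of the observed AEs". It lists severity, relatedness and overall incidence as distinct kinds of table. SAP Section 5 sets the denominator for solicited AEs as "those subjects in the FA set for whom reactogenicity assessments are available in the database", and the per-dose tables divide by all doses given of the vaccine concerned.

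Protocol Section 11.5 brings all reported AEs with onset in the treatment period into the analysis. It names solicited events explicitly and counts subjects with one occurrence or more, with exact 95% confidence intervals by group. It attaches no condition about grade.

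Protocol Section 9.3.1 lists "local and systemic reactogenicity rates for 8 days after each vaccination" among the safety and tolerability endpoints, and SAP Section 5 does the same. Safety and tolerability is a primary objective in Protocol Section 2.1.

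**The concern.** A missing grade says nothing about whether the event happened. A subject who reported, say, erythema with no severity recorded is known to have had erythema. If the record is set aside for every table, the any-grade row treats that subject as having had none. Despite the statement that nothing is imputed, the effect in that row is the same as imputing no event.

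The error runs in one direction, towards better apparent tolerability. It would reach the tables by regimen, by vaccine and by dose. Reactogenicity also bears on the choice of regimen, because Protocol Section 11 says the Week 28 analysis supports that choice on immunogenicity and safety together.

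**Working it through.** **1. The plan's own figures.** The plan states no reactogenicity rate, so there is none to reproduce. Its nearest safety figures are in Protocol Section 11.2, and they hold. With 0 events in 50 subjects the 95% upper limit is 1 − 0.05^(1/50) = 5.8% (stated: under 6%). With 0 in 350 it is 0.85% (stated: under 1%). None of these depends on the missing-severity rule.

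**2. Numerator and denominator.**
- Numerator (SAP 5.1.2): subjects with at least one event. SAP 5.1.4 takes out events without a grade.
- Denominator (SAP 5): subjects with any reactogenicity assessment, or all doses given. A missing grade removes neither the subject nor the dose.
- No section returns the event to the any-grade, relatedness or overall incidence tables. No row for unknown severity and no sensitivity analysis is planned.

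**3. Size.** Let p be the true any-grade incidence of a term in a period. Let m be the share of affected subjects whose only records of that term in that period are ungraded. The reported incidence is p × (1 − m) and the loss is p × m, which is never negative. The documents give neither p nor m, so the values below are assumptions.

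| True p | m = 0 | m = 2% | m = 5% | m = 10% | m = 20% |
|---|---|---|---|---|---|
| 20% | 20.0% | 19.6% | 19.0% | 18.0% | 16.0% |
| 60% | 60.0% | 58.8% | 57.0% | 54.0% | 48.0% |
| 80% | 80.0% | 78.4% | 76.0% | 72.0% | 64.0% |

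**4. One group of 50.** Suppose 30 subjects are affected and 3 have only ungraded records. Under the rule the table shows 27/50 = 54.0% (exact 95% CI 39.3 to 68.2). Counting all reported events gives 30/50 = 60.0% (45.2 to 73.6).

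**5. Contrast with placebo.** With the same m in both groups, the reported difference is (p1 − p0) × (1 − m). For assumed rates of 60% and 20% and m = 10%, it is 54.0 − 18.0 = 36 points instead of 40. Equal missingness does not cancel out.

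**6. How the SAP treats other missing attributes.**
- Injection site not linked (Section 5): the local AE counts for both products.
- Partial dates (Section 5.1.3): the event is kept, even if it then falls in several periods.
- Laboratory baseline missing (Section 5.2): the abnormality is kept as emergent.

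The solicited-severity rule is the exception, and it goes in the less cautious direction.

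**The case against.** The best counter-argument is grammatical: it is the severity that is unknown, so perhaps only the severity is set aside and the event still counts. The general counting rule in SAP 5.1.2, "number and percentage of subjects having at least one of the observed AEs", requires no grade. This reading is possible, but the SAP never says so, and the specific rule ends with exclusion from the analysis as a whole. If severity tables were all that was meant, the fix below simply makes that explicit.

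It could also be said that few grades will be missing. AEs are to be graded (Protocol 12.1.3), site staff go through the memory aid with the subject (9.3.2), and CRF entries can be queried (17.5). That stands as a reason to expect a small effect. Daily recording helps too, since one graded record of the term in the period is enough to keep the subject in the numerator. One route to missing grades stays open: in Attachment 1, erythema and induration/swelling are graded only from 2.5 cm, and the documents do not say how smaller reported reactions are coded.

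Safety is descriptive and the rule is the same in all groups. Both points are true, but the descriptive rates are what this analysis delivers, and a common rule still shrinks contrasts, as step 5 shows. Dropping the affected subjects from the denominator as well would not cure it: 27/47 = 57.4%, still below 60.0%.

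Two further inferences are tempting. A reader might call reactogenicity the primary safety endpoint, but the documents list it among safety and tolerability endpoints under a primary objective and do not use that label. A reader might also want ungraded events counted as Grade 3 in a sensitivity analysis. Nothing in the documents supports that, and if the ungraded events are reactions under 2.5 cm it would turn the mildest into severe ones.

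**Conclusion.** The point holds as a conflict between SAP 5.1.4 and Protocol 11.5 whose effect has a known direction and an unknown size. Read plainly, the SAP rule can only lower any-grade reactogenicity. The loss is p × m: from 0 up to 16 percentage points for p up to 80% and m up to 20%, both assumed. It is exactly zero if every solicited AE has a grade, or if each affected subject has another graded record of the same term in the period.

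A reader might infer that the trial's reactogenicity has been understated. The documents do not support that, because they do not show that any solicited AE lacked a grade.

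**What to change.** Amend SAP 5.1.4 so that the exclusion applies only to summaries by grade. State that every reported solicited AE counts in the any-grade and overall incidence tables, and in relatedness tables where relatedness is known. Under SAP 5.1.1 that is always so for local solicited AEs. Add a row for unknown severity to the by-grade tables. On paper this costs one sentence and one table row.

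The new wording alone will not change any solicited-AE table. SAP Section 1 says the Week 96 analysis had been run before this SAP version and is not to be repeated. The last vaccination is at Week 48, so all solicited AEs fall within that analysis, and the extension collects only SAEs and HIV infections. The study report should therefore give, per group, the number of ungraded solicited AEs that were excluded. If there were none, a sentence saying so closes the matter. If there were some, the report should give corrected any-grade counts for the terms and periods affected. The cost is one query of the existing data and, at most, a short supplementary table.
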